6.2 DATA SHARING PLANS

6.2.1 Human Data Sharing Plan

What data will be shared?

I will share human data generated in this research for future research as follows:

- Coded, linked data in an NIH-funded or approved public repository.
- Coded, linked data in BTRIS (automatic for activities in the Clinical Center)
- Identified or coded, linked data with approved outside collaborators under appropriate agreements.

How and where will the data be shared?

Data will be shared through:

- An NIH-funded or approved public repository: clinicaltrials.gov, dbGaP

Abbreviated Title: Prostvac-Nivo in prostate ca

Version Date: 01.10.2023

- BTRIS (automatic for activities in the Clinical Center)
- Approved outside collaborators under appropriate individual agreements.
- Publication and/or public presentations.

When will the data be shared?

- Before publication.
- At the time of publication or shortly thereafter.

6.2.2 Genomic Data Sharing Plan

Unlinked genomic data will be deposited in public genomic databases such as dbGaP in compliance with the NIH Genomic Data Sharing Policy.

6.3 RESPONSE CRITERIA (APPLICABLE TO CRPC COHORT)

Recent clinical studies evaluating checkpoint inhibitors in solid tumors have shown that in a fraction of cases even if some new lesions appear at the beginning of a treatment or if the total tumor burden does not increase substantially, tumor regressions or stabilizations might still occur later. For the CRPC cohort of this trial, a modified immune related response criteria (irRC) based on RECIST 1.1 [44] will be used (See Appendix D, Section 16.4). Changes in the largest diameter (unidimensional measurement) of the tumor lesions and the shortest diameter in the case of malignant lymph nodes will be used as per RECIST 1.1 criteria.

This modified irRC will be based upon RECIST 1.1 criteria (described below) except for 2 major changes:

- 1) require confirmation of progression by imaging at 4 weeks after initial imaging (evidence of progression of prostate cancer within the first 3 months on bone scan only should be interpreted with extreme caution due to risk of tumor flare) and
- 2) do not necessarily score the appearance of new lesions as progressive disease if the sum of lesion diameters of target lesions (minimum of 10 mm per lesion, maximum of 5 target lesions, maximum of 2 per organ) and measurable new lesions does not increase by $\geq 20\%$.

6.3.1 Definitions

Evaluable for toxicity: All participants will be evaluable for toxicity from the time of their first treatment

Evaluable for objective response: Only those participants who have measurable disease present at baseline, have received at least one cycle of therapy, and have had their disease re-evaluated will be considered evaluable for response. These participants will have their response classified according to the definitions stated below. (Note: Participants who exhibit objective disease progression prior to the end of cycle 1 will also be considered evaluable.)

Evaluable Non-Target Disease Response: Participants who have lesions present at baseline that are evaluable but do not meet the definitions of measurable disease, have received at least one cycle of therapy, and have had their disease re-evaluated will be considered evaluable for non-

target disease. The response assessment is based on the presence, absence, or unequivocal progression of the lesions.

6.3.2 Disease Parameters

Measurable disease: Measurable lesions are defined as those that can be accurately measured in at least one dimension (longest diameter to be recorded) as:

- By chest x-ray: ≥ 20 mm;
- By CT scan:
 - .1 Scan slice thickness 5 mm or under: as ≥ 10 mm;
 - .2 Scan slice thickness >5 mm: double the slice thickness
- With calipers on clinical exam: ≥ 10 mm.

All tumor measurements must be recorded in millimeters (or decimal fractions of centimeters).

Malignant lymph nodes. To be considered pathologically enlarged and measurable, a lymph node must be ≥ 15 mm in short axis when assessed by CT scan (CT scan slice thickness recommended to be no greater than 5 mm). At baseline and in follow-up, only the short axis will be measured and followed.

Non-measurable disease. All other lesions (or sites of disease), including small lesions (longest diameter <10 mm or pathological lymph nodes with ≥ 10 to <15 mm short axis), are considered non-measurable disease. Bone lesions, leptomeningeal disease, ascites, pleural/pericardial effusions, lymphangitis cutis/pulmonitis, inflammatory breast disease, and abdominal masses (not followed by CT or MRI), are considered as non-measurable.

Note: Cystic lesions that meet the criteria for radiographically defined simple cysts should not be considered as malignant lesions (neither measurable nor non-measurable) since they are, by definition, simple cysts.

‘Cystic lesions’ thought to represent cystic metastases can be considered as measurable lesions, if they meet the definition of measurability described above. However, if non-cystic lesions are present in the same participant, these are preferred for selection as target lesions.

Target lesions. All measurable lesions up to a maximum of 2 lesions per organ and 5 lesions in total, representative of all involved organs, should be identified as **target lesions** and recorded and measured at baseline. Target lesions should be selected on the basis of their size (lesions with the longest diameter), be representative of all involved organs, but in addition should be those that lend themselves to reproducible repeated measurements. It may be the case that, on occasion, the largest lesion does not lend itself to reproducible measurement in which circumstance the next largest lesion which can be measured reproducibly should be selected. A sum of the diameters (longest for non-nodal lesions, short axis for nodal lesions) for all target lesions will be calculated and reported as the baseline sum diameters. If lymph nodes are to be included in the sum, then only the short axis is added into the sum. The baseline sum diameters will be used as reference to further characterize any objective tumor regression in the measurable dimension of the disease.

Non-target lesions. All other lesions (or sites of disease) including any measurable lesions over and above the 5 target lesions should be identified as **non-target lesions** and should also be recorded at baseline. Measurements of these lesions are not required, but the presence, absence, or in rare cases unequivocal progression of each should be noted throughout follow-up.

6.3.3 Methods for Evaluation of Measurable Disease

All measurements should be taken and recorded in metric notation using a ruler or calipers. All baseline evaluations should be performed as closely as possible to the beginning of treatment and never more than 8 weeks before the beginning of the treatment.

The same method of assessment and the same technique should be used to characterize each identified and reported lesion at baseline and during follow-up. Imaging-based evaluation is preferred to evaluation by clinical examination unless the lesion(s) being followed cannot be imaged but are assessable by clinical exam.

Clinical lesions: Clinical lesions will only be considered measurable when they are superficial (e.g., skin nodules and palpable lymph nodes) and ≥ 10 mm diameter as assessed using calipers (e.g., skin nodules). In the case of skin lesions, documentation by color photography, including a ruler to estimate the size of the lesion, is recommended.

Chest x-ray: Lesions on chest x-ray are acceptable as measurable lesions when they are clearly defined and surrounded by aerated lung. However, CT is preferable.

Conventional CT and MRI: This guideline has defined measurability of lesions on CT scan based on the assumption that CT slice thickness is 5 mm or less. If CT scans have slice thickness greater than 5 mm, the minimum size for a measurable lesion should be twice the slice thickness. MRI is also acceptable in certain situations (e.g. for body scans).

Use of MRI remains a complex issue. MRI has excellent contrast, spatial, and temporal resolution; however, there are many image acquisition variables involved in MRI, which greatly impact image quality, lesion conspicuity, and measurement. Furthermore, the availability of MRI is variable globally. As with CT, if an MRI is performed, the technical specifications of the scanning sequences used should be optimized for the evaluation of the type and site of disease. Furthermore, as with CT, the modality used at follow-up should be the same as was used at baseline and the lesions should be measured/assessed on the same pulse sequence. It is beyond the scope of the RECIST guidelines to prescribe specific MRI pulse sequence parameters for all scanners, body parts, and diseases. Ideally, the same type of scanner should be used and the image acquisition protocol should be followed as closely as possible to prior scans. Body scans should be performed with breath-hold scanning techniques, if possible.

PET-CT: At present, the low dose or attenuation correction CT portion of a combined PET-CT is not always of optimal diagnostic CT quality for use with RECIST measurements. However, if the site can document that the CT performed as part of a PET-CT is of identical diagnostic quality to a diagnostic CT (with IV and oral contrast), then the CT portion of the PET-CT can be used for RECIST measurements and can be used interchangeably with conventional CT in accurately measuring cancer lesions over time. Note, however, that the PET portion of the CT introduces additional data which may bias an investigator if it is not routinely or serially performed.

Ultrasound: Ultrasound is not useful in assessment of lesion size and should not be used as a method of measurement. Ultrasound examinations cannot be reproduced in their entirety for independent review at a later date and, because they are operator dependent, it cannot be guaranteed that the same technique and measurements will be taken from one assessment to the next. If new lesions are identified by ultrasound in the course of the study, confirmation by CT or MRI is advised. If there is concern about radiation exposure at CT, MRI may be used instead of CT in selected instances.

Endoscopy, Laparoscopy: The utilization of these techniques for objective tumor evaluation is not advised. However, such techniques may be useful to confirm complete pathological response when biopsies are obtained or to determine relapse in trials where recurrence following complete response (CR) or surgical resection is an endpoint.

Tumor markers: Tumor markers alone cannot be used to assess response. If markers are initially above the upper normal limit, they must normalize for a participant to be considered in complete clinical response. Specific guidelines for both CA-125 response (in recurrent ovarian cancer) and PSA response (in recurrent prostate cancer) have been published. [45-47] In addition, the Gynecologic Cancer Intergroup has developed CA-125 progression criteria which are to be integrated with objective tumor assessment for use in first-line trials in ovarian cancer.[48]

Cytology, Histology: These techniques can be used to differentiate between partial responses (PR) and complete responses (CR) in rare cases (e.g., residual lesions in tumor types, such as germ cell tumors, where known residual benign tumors can remain).

The cytological confirmation of the neoplastic origin of any effusion that appears or worsens during treatment when the measurable tumor has met criteria for response or stable disease is mandatory to differentiate between response or stable disease (an effusion may be a side effect of the treatment) and progressive disease.

FDG-PET: While FDG-PET response assessments need additional study, it is sometimes reasonable to incorporate the use of FDG-PET scanning to complement CT scanning in assessment of progression (particularly possible 'new' disease). New lesions on the basis of FDG-PET imaging can be identified according to the following algorithm:

- Negative FDG-PET at baseline, with a positive FDG-PET at follow-up is a sign of PD based on a new lesion.
- No FDG-PET at baseline and a positive FDG-PET at follow-up: If the positive FDG-PET at follow-up corresponds to a new site of disease confirmed by CT, this is PD. If the positive FDG-PET at follow-up is not confirmed as a new site of disease on CT, additional follow-up CT scans are needed to determine if there is truly progression occurring at that site (if so, the date of PD will be the date of the initial abnormal FDG-PET scan). If the positive FDG-PET at follow-up corresponds to a pre-existing site of disease on CT that is not progressing on the basis of the anatomic images, this is not PD.
- FDG-PET may be used to upgrade a response to a CR in a manner similar to a biopsy in cases where a residual radiographic abnormality is thought to represent fibrosis or scarring. The use of FDG-PET in this circumstance should be prospectively described in the protocol and supported by disease-specific medical literature for the indication. However, it must be acknowledged that both approaches may lead to false positive CR due to limitations of FDG-PET and biopsy resolution/sensitivity.

Note: A ‘positive’ FDG-PET scan lesion means one which is FDG avid with an uptake greater than twice that of the surrounding tissue on the attenuation corrected image.

6.3.4 Response Criteria

6.3.4.1 Evaluation of Target Lesions

Complete Response (CR): Disappearance of all target lesions. Any pathological lymph nodes (whether target or non-target) must have reduction in short axis to <10 mm.

Partial Response (PR): At least a 30% decrease in the sum of the diameters of target lesions, taking as reference the baseline sum of diameters.

Progressive Disease (PD): At least a 20% increase in the sum of the diameters of target lesions, taking as reference the smallest sum on study (this includes the baseline sum if that is the smallest on study). In addition to the relative increase of 20%, the sum must also demonstrate an absolute increase of at least 5 mm. (Note: the appearance of one or more new lesions is also considered progressions).

Stable Disease (SD): Neither sufficient shrinkage to qualify for PR nor sufficient increase to qualify for PD, taking as reference the smallest sum of diameters while on study.

6.3.4.2 Evaluation of Non-Target Lesions

Complete Response (CR): Disappearance of all non-target lesions and normalization of tumor marker level. All lymph nodes must be non-pathological in size (<10 mm short axis).

Note: If tumor markers are initially above the upper normal limit, they must normalize for a participant to be considered in complete clinical response.

Non-CR/Non-PD: Persistence of one or more non-target lesion(s) and/or maintenance of tumor marker level above the normal limits.

Progressive Disease (PD): Appearance of one or more new lesions and/or *unequivocal progression* of existing non-target lesions. *Unequivocal progression* should not normally trump target lesion status. It must be representative of overall disease status change, not a single lesion increase.

Although a clear progression of “non-target” lesions only is exceptional, the opinion of the treating physician should prevail in such circumstances, and the progression status should be confirmed at a later time by the review panel (or Principal Investigator).

6.3.4.3 Metastatic Bone Lesions

Disease progression is considered if a minimum of two new lesions is observed on bone scan.

6.3.4.4 Evaluation of Best Overall Response

The best overall response is the best response recorded from the start of the treatment until disease progression/recurrence (taking as reference for progressive disease the smallest measurements recorded since the treatment started). The participant's best response assignment will depend on the achievement of both measurement and confirmation criteria.

For Participants with Measurable Disease (i.e., Target Disease)

Target Lesions	Non-Target Lesions	New Lesions	Overall Response	Best Overall Response when Confirmation is Required*
CR	CR	No	CR	≥ 4 wks. Confirmation**
CR	Non-CR/Non-PD	No	PR	≥ 4 wks. Confirmation**
CR	Not evaluated	No	PR	
PR	Non-CR/Non-PD/not evaluated	No	PR	
SD	Non-CR/Non-PD/not evaluated	No	SD	Documented at least once ≥ 4 wks. from baseline**
PD	Any	Yes or No	PD	no prior SD, PR or CR
Any	PD***	Yes or No	PD	
Any	Any	Yes	PD	

* See RECIST 1.1 manuscript for further details on what is evidence of a new lesion.
** Only for non-randomized trials with response as primary endpoint.
*** In exceptional circumstances, unequivocal progression in non-target lesions may be accepted as disease progression.

Note: Participants with a global deterioration of health status requiring discontinuation of treatment without objective evidence of disease progression at that time should be reported as “*symptomatic deterioration*.” Every effort should be made to document the objective progression even after discontinuation of treatment.

For Participants with Non-Measurable Disease (i.e., Non-Target Disease)

Non-Target Lesions	New Lesions	Overall Response
--------------------	-------------	------------------

CR	No	CR
Non-CR/non-PD	No	Non-CR/non-PD*
Not all evaluated	No	not evaluated
Unequivocal PD	Yes or No	PD
Any	Yes	PD

* 'Non-CR/non-PD' is preferred over 'stable disease' for non-target disease since SD is increasingly used as an endpoint for assessment of efficacy in some trials so to assign this category when no lesions can be measured is not advised

6.3.5 Duration of Response

Duration of overall response: The duration of overall response is measured from the time measurement criteria are met for CR or PR (whichever is first recorded) until the first date that recurrent or progressive disease is objectively documented (taking as reference for progressive disease the smallest measurements recorded since the treatment started).

The duration of overall CR is measured from the time measurement criteria are first met for CR until the first date that progressive disease is objectively documented.

Duration of stable disease: Stable disease is measured from the start of the treatment until the criteria for progression are met, taking as reference the smallest measurements recorded since the treatment started, including the baseline measurements.

6.3.6 Progression-Free Survival

6.3.6.1 Serologic Response

PSA will be assessed at each visit during treatment and every 12 weeks thereafter. Participants will be assigned response based on the following criteria.

Complete Serological Response: PSA level less than 0.2 ng/ml measured for 2 consecutive measurements at least 4 weeks apart.

Serological Partial Response: decline of PSA at least 50% measured for 2 consecutive measurements at least 4 weeks apart.

Serological Progression:

- Serological progression will only be measured once PSA has risen above 4 ng/ml and this value must be 50% above the PSA level before commencing ADT and;
- Increase in PSA more than 50% of nadir (lowest PSA on ADT).
- Values must be measured for 2 consecutive measurements at least 2 weeks apart.
- The date of the first increase will be recorded as progression.

Abbreviated Title: Prostvac-Nivo in prostate ca

Version Date: 01.10.2023

Time to Serologic Progression will be defined as interval between initiation of ADT and date of PSA progression or death from any cause.

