f. creatinine	$\leq 1.5 \times \text{ULN}$

2.1.1.9 For the lead in cohort:

- Castrate testosterone level ($<50\text{ng/dl}$ or 1.7nmol/L)
- Progressive disease at study entry defined as one or more of the following criteria occurring in the setting of castrate levels of testosterone:

- Radiographic progression defined as **any new** or enlarging bone lesions or growing lymph node disease, consistent with prostate cancer

OR

- PSA progression defined by sequence of rising values separated by >1 week (2 separate increasing values over a minimum of 2ng/ml (PCWG2 PSA eligibility criteria). If participants had been on flutamide, PSA progression is documented 4 weeks or more after withdrawal. For participants on bicalutamide or nilutamide disease progression is documented 6 or more weeks after withdrawal.
- Participants must agree to continuation of androgen deprivation therapy (ADT) with a gonadotropin-releasing hormone agonist/antagonist or bilateral orchiectomy

2.1.1.10 For the neoadjuvant cohort:

1. Participants must be a surgical candidate for radical prostatectomy based on standard workup of PSA, biopsy results, and if necessary supplemental imaging.
2. Participants must have chosen radical prostatectomy as their definitive treatment of choice for management of their prostate cancer as part of their standard of care treatment.
3. No systemic steroid or steroid eye drop use within 2 weeks prior to initiation of experimental therapy. Limited doses of systemic steroids to prevent IV contrast, allergic reaction or anaphylaxis (in participants who have known contrast allergies) are allowed.

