3.3 DOSE MODIFICATIONS

Participants must have recovered to \leq grade 1 attributable toxicity for the parameters used to assess levels of organ function required for eligibility (see Section 2.1) after each treatment in order to receive a subsequent treatment. Participants who experience irAE may continue PROSTVAC alone if irAE appears to be driven by nivolumab. In such circumstances, investigator will discuss fully the potential risks with the participant and document that conversation appropriately. Any dosing interruption lasting > 6 weeks from the last dose will require participants to be removed from protocol with the following exceptions:

- Dosing interruptions to allow for prolonged steroid tapers to manage drug-related adverse events are allowed. Tumor imaging assessments should continue as per protocol even if dosing is interrupted
- Dosing interruptions > 6 weeks from the last dose that occur for non-drug-related reasons may be allowed
- For subjects with mCRPC who have stopped receiving nivolumab because of grade 3 or higher irAEs, nivolumab could be re-started if the participant had partial response according Prostate Cancer Working Group 3 (PCWG 3) and RECIST 1.1 criteria but subsequently develops PSA progression (by PCWG 3) while on PROSTVAC alone.

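### In the CRPC lead-in cohort, time to serologic progression is anchored to the start of ADT, which precedes enrolment for every participant, so it does not measure the study treatment

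*Combined protocol and SAP*

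**What the plan says.** Section 6.3 restricts its response criteria to the CRPC cohort. For those men, section 2.1.1.9 requires castrate testosterone and "Progressive disease at study entry defined as one or more of the following criteria occurring in the setting of castrate levels of testosterone". It adds: "Participants must agree to continuation of androgen deprivation therapy (ADT) with a gonadotropin-releasing hormone agonist/antagonist or bilateral orchiectomy".

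Section 6.3.6.1 then defines serological progression by several conditions:

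- PSA must exceed 4 ng/ml, and "this value must be 50% above the PSA level before commencing ADT and" a further condition must hold.
- That further condition reads "Increase in PSA more than 50% of nadir (lowest PSA on ADT", with the bracket closing after ADT.
- A second value is needed two weeks or more later, and the event is dated back to the initial rise.

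The time variable is defined as follows: "Time to Serologic Progression will be defined as interval between initiation of ADT and date of PSA progression or death from any cause".

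Two other places bear on this. Section 6.3.5 times stable disease from the start of treatment and takes its reference measurements from that point. Section 3.3 allows nivolumab to be restarted in a participant who, among other conditions, "subsequently develops PSA progression (by PCWG 3) while on PROSTVAC alone".

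**The concern.** The serologic rule fits a trial that starts ADT. This trial does not: every man in the cohort began ADT, or had an orchiectomy, before he enrolled. The rule therefore takes its time origin and one of its PSA reference values from his earlier treatment history.

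Three things follow. The reported interval mixes pre-study and on-study time. Because death counts as an event, part of that interval carries guaranteed survival. And whether an on-study PSA rise counts depends on a PSA value that may be years old. The only PSA objective, in section 1.1.2, is to describe changes due to the immune treatment, and an interval that opens before that treatment cannot do so.

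There is also a practical problem. Neither the pre-ADT PSA nor the ADT start date is named among the screening or baseline items in sections 2.1.4.1, 2.3.1 and 3.5.1. They may be recoverable from the medical history, but nothing says they will be collected.

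**Working it through.** The plan states no figure for this endpoint, so there is none to reproduce. The contradiction comes from reading sections 2.1.1.9 and 6.3.6.1 together. The arithmetic below only shows its possible size. **All PSA values, ADT durations and doubling times are assumptions**, because the documents give none.

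**1. Time origin.** Reported time = ADT months before enrolment + on-study months. Share before enrolment = ADT months / reported time.

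| ADT before entry | On-study progression | Reported time | Share before enrolment |
|---|---|---|---|
| 12 months | 3 months | 15 months | 12/15 = 80% |
| 12 months | 6 months | 18 months | 12/18 = 67% |
| 60 months | 3 months | 63 months | 60/63 = 95% |
| 60 months | 6 months | 66 months | 60/66 = 91% |

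Timed from first study treatment, the same men would show 3 or 6 months.

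**2. Threshold.** The level conditions are joined by 'and', so all must hold:

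threshold = max(4, 1.5 × pre-ADT PSA, 1.5 × lowest PSA on ADT).

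Whenever the nadir is at or below the pre-ADT PSA, 1.5 × nadir cannot exceed 1.5 × pre-ADT PSA. The nadir condition then adds nothing, and the pre-ADT value (or the 4 ng/ml floor) decides.

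- *High pre-ADT PSA.* Pre-ADT 40, nadir 0.5, entry 8: max(4, 60, 0.75) = 60 ng/ml. PSA must rise 60/8 = 7.5-fold on study before anything is scored.
- *Range at entry PSA 10.* Pre-ADT 20, 50 or 100 gives thresholds of 30, 75 or 150, that is, 3-, 7.5- or 15-fold.
- *Low pre-ADT PSA.* Pre-ADT 5, nadir 1, entry 10: max(4, 7.5, 1.5) = 7.5 ng/ml. The man is above the threshold at entry. Subject to the confirming value, his event may be dated at or before week 0.

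**3. Delay from the threshold.** Time to threshold = doubling time × log2(threshold / entry PSA). With a 3-month doubling time and entry PSA 10:

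- 50% rise from entry (15 ng/ml): 3 × log2(1.5) = 1.8 months
- pre-ADT 20 (threshold 30): 3 × log2(3) = 4.8 months
- pre-ADT 50 (threshold 75): 3 × log2(7.5) = 8.7 months

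**4. Same men, references taken from study entry.** If PSA does not fall on study, a 50% rise over the on-study nadir is 1.5 × 8 = 12 ng/ml in the first example and 1.5 × 10 = 15 ng/ml in the low pre-ADT example. Neither threshold is met at entry, and neither needs a several-fold rise.

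**The case against.** The strongest reply concerns consequence. Time to serologic progression is not a named objective and does not appear in section 10. The cohort has 10 men, no comparator and safety as its primary objective. Removal from therapy for progression (section 3.7.1) rests on clinical findings or confirmed imaging, not PSA. The restart provision in section 3.3 names its own standard. No test, sample size or go/no-go decision uses section 6.3.6.1. All of this stands, and it limits the severity.

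It can also be said that the sizes above follow from the values chosen. That is true of the sizes, but not of the mismatch between the rule and the population.

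A reader might be tempted to go further in four ways that the documents do not support:

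- *That everyone is progression-free by construction up to entry.* Entry requires progression. Only survival to enrolment is guaranteed, and some men may already meet the serologic rule.
- *That the rule must flatter the combination.* The early clock lengthens the time for events that occur on study, but the threshold can delay an event or place it at or before week 0. The net direction is unknown.
- *That the nadir always predates the study.* ADT continues on study, so a responder's lowest PSA on ADT can fall after week 0.
- *That the PCWG2 rule at eligibility conflicts with section 6.3.6.1.* It defines progression for entry, which is a different purpose. The mismatch is between sections 3.3 and 6.3.6.1, which both concern PSA progression on study.

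**Conclusion.** The definition is wrong as written for this cohort, and no other section repairs it. For every participant the clock starts before enrolment, so the result would not be interpretable as an effect of PROSTVAC plus nivolumab. The pre-ADT threshold adds misclassification in both directions.

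That conclusion rests on the text alone. The 67% to 95% share depends on the assumed 12 to 60 months of earlier ADT and 3 to 6 months on study. The threshold examples depend on the assumed PSA values.

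The severity is should-fix. Neither the lead-in safety decision nor the neoadjuvant T-cell comparison is affected.

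**What to change.** In section 6.3.6.1:

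1. Start the clock at first study treatment (week 0).
2. Take the last PSA before week 0 as baseline, and define nadir as the lowest PSA from baseline onward.
3. Drop the condition tied to the pre-ADT PSA.
4. State that the 50% decline for serologic partial response is measured from the same baseline; the section currently names no reference for it.
5. Reconcile this endpoint definition with the PCWG 3 PSA progression named in section 3.3, leaving the treatment provision there as it is. The documents do not spell out the PCWG 3 rule, so the definition adopted for the endpoint should be written out in full.

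The change is to wording. Baseline and on-treatment PSA are already scheduled in sections 2.3.1 and 3.5.1, and the pre-ADT PSA and ADT start date would no longer be needed for this measure. One gap remains: section 6.3.6.1 promises PSA every 12 weeks after treatment, but the lead-in calendar schedules no PSA beyond the safety visit at 4 to 5 weeks. The text should say how long PSA is followed and how men without an event are censored. The visible cost is that reported times become much shorter.
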